8.3.7 Non-Serious Adverse Events of Special Interest

Adverse events of special interest are required to be reported by the Investigator to the Sponsor immediately (i.e., no more than 24 hours after learning of the event; see [Appendix 10](#) for reporting instructions).

Adverse events of special interest for this study include the following:

- Cases of an elevated ALT or AST in combination with either an elevated bilirubin or clinical jaundice, as defined in [Appendix 11](#).
- Suspected transmission of an infectious agent by the study treatment, as defined below:
 - Any organism, virus, or infectious particle (e.g., prion protein transmitting transmissible spongiform encephalopathy), pathogenic or non-pathogenic, is considered an infectious agent. A transmission of an infectious agent may be suspected from clinical symptoms or laboratory findings that indicate an infection in a patient exposed to a medicinal product. This term applies only when a contamination of the study treatment is suspected.
- Thromboembolic events (Grade ≥ 2) are of particular interest for the PV population and should be reported to the Sponsor.
- Grade 3 or 4 (or any grade in presence of bleeding) thrombocytopenia (refer to [Appendix 12](#) for a list of example Preferred Terms considered pertinent to thrombocytopenia)
- Grade ≥ 3 systemic infection;
- Grade ≥ 3 GI toxicity (refer to [Appendix 12](#) for the list of PT considered pertinent to GI toxicity);
- Any grade supraventricular arrhythmias (MedDRA PT reported included in the Supraventricular tachyarrhythmias (refer to [Appendix 12](#) for a list of example Preferred Terms considered pertinent to Supraventricular tachyarrhythmias).

8.3.8 Disease-Related Events and/or Disease-Related Outcomes Not Qualifying as AEs or SAEs

The following disease-related events (DREs) are common in patients with PV and can be serious/life-threatening:

- Fever, in the absence of neutropenia
- Abdominal swelling without known organomegaly
- Pruritus
- Fatigue
- Early satiety

- Night sweats
- Splenomegaly

If present at baseline and related to PV, the event should be added to the PV Medical History eCRF and marked as ongoing with or without treatment, indicating any ongoing treatments on the Previous and Concomitant Treatments (Targeted - Polycythemia Vera Associated) eCRF.

Because these events are typically associated with the disease under study, they will not be reported as AEs or according to the standard process for expedited reporting of SAEs even though the event may meet the definition of a SAE.

NOTE: However, if either of the following conditions applies, then the event must be recorded and reported as an SAE (instead of a DRE):

- The event is, in the Investigator's opinion, of greater intensity, frequency, or duration than expected for the individual patient.

OR

- The Investigator considers that there is a reasonable possibility that the event was related to treatment with the investigational product.

Events considered related to PV will instead be recorded on the PV Medical History eCRF with any treatments administered noted on the Previous and Concomitant Treatments (Targeted - Polycythemia Vera Associated) eCRF. In the event that a patient achieves a CHR at Week 32, then subsequent episodes of these events should be reported as AEs.

These DREs will be reviewed by the Medical Monitor.

8.3.9 Management of Specific Adverse Events

The safety profile of idasanutlin is currently available at higher dose regimens than those to be investigated in this study *and primarily based on patients with solid tumor or AML*. At such higher doses the following identified risks are present: diarrhea; nausea; vomiting; decreased appetite/anorexia; fatigue/asthenia; thrombocytopenia and increased hemorrhagic risk; neutropenia and febrile neutropenia; anemia; pyrexia; sepsis; pneumonia; fungal infections; electrolyte disorders; tumor lysis syndrome. Thrombocytopenia and GI toxicity are dose/exposure dependent but are not expected to occur as severe events at the dose levels investigated in this study. In case of occurrence of events different from those outlined below, guidelines to manage the risk can be found in the [Idasanutlin IB](#).

8.3.9.1 Management of Gastrointestinal Toxicity (Diarrhea, Nausea and Vomiting)

GI toxicity has early onset and occurs frequently within hours from dosing. Nausea and vomiting are common events secondary to idasanutlin treatment. Appropriate

mandatory anti-emetic prophylaxis is described in Section 6.1.1. Rescue medication may include blockers of neurokinin 1 receptor (NK-1 RA; *aprepitant 125 mg orally on Day 1, then 80 mg orally daily, fosaprepitant 150 mg IV on Day 1 or switch to oral fixed-combination netupitant/palonosetron [dexamethasone dose should be adjusted if netupitant/palonosetron is administered]*). It is recommended to administer IV fluids and correct electrolytes as clinically required.

Diarrhea is also commonly reported in patients treated with idasanutlin. Specific guidelines to manage this risk are summarized in [Table 7](#).

Table 7 Guidelines for Managing Diarrhea

Event	Action to Be Taken
Grade 1–2 diarrhea	
Rule out other or concomitant causes, including medications (e.g., stool softeners, laxatives, antacids), malabsorption/lactose intolerance, fecal impaction, and dietary supplements high in fiber.
 
Dietary modifications:
 
 - Stop all lactose-containing products and eat small meals. - The BRAT (banana, rice, apples, toast) diet may be helpful. - Encourage adequate hydration. 
Loperamide treatment
 
 - Suggested initial dose of 4 mg followed by 2 mg every 4 hours or after every unformed stool; up to a maximum of 16 mg/day. - Recommend to continue loperamide treatment until diarrhea-free for 24 hours. - If Grade ≤ 2 diarrhea persists after 48 hours total treatment with loperamide, consider second-line agents (diphenoxylate and atropine, octreotide, budesonide, or tincture of opium). 
No change in study drug dosing will be implemented for Grade ≤ 2 diarrhea; patients should receive maximal supportive care as described above. If the event Grade ≥ 2 occurs, patients will be advised to undergo antidiarrheal prophylaxis for subsequent cycles.

Grade ≥ 3 diarrhea	
If Grade ≥ 3 diarrhea occurs despite adequate supportive care, then all study drugs should be held until the diarrhea has improved to Grade ≤ 1.
 
 - If recovery occurs within 28 days, study drugs may be re-started with idasanutlin with a 50 mg dose reduction (lowest idasanutlin dose is 100 mg), with continued supportive care or prophylaxis. - If bowel movement characteristics have NOT improved to Grade ≤ 1 or baseline with maximal supportive care by 28 days, then idasanutlin should be permanently discontinued. 
If Grade ≥ 3 diarrhea recurs despite supportive care and idasanutlin dose-reduction, all study drug should be held until the diarrhea resolves to Grade ≤ 1.
 
 - If recovery occurs within 28 days, then the idasanutlin dose will be maintained at the previously reduced dose of 100 mg. If recovery is >28 days, idasanutlin should be permanently discontinued. 
If the diarrhea recurs at Grade ≥ 3, idasanutlin should be permanently discontinued.

In order to reduce the risk of developing diarrhea, patients should be carefully screened for active GI conditions including uncontrolled bowel disease (i.e., Crohn disease, ulcerative colitis, diverticulosis associated colitis, and Behçet's disease). Patients with active GI conditions at screening should be excluded from treatment with idasanutlin as per Section 5.2.

Prophylactic antidiarrheal regimen has shown efficacy in moderating symptoms in AML patients treated with higher doses of idasanutlin. Antidiarrheal therapy is recommended as prophylaxis for all patients who manifested Grade ≥ 2 diarrhea during a previous cycle. An oral loading dose of 4 mg loperamide 30 minutes before the administration of study medication has proven to be effective for managing the severity of diarrhea.

If diarrhea occurs, 2 mg loperamide should be administered orally every 4 hours or after every unformed stool to a maximum dose of 16 mg per 24 hours. It is recommended to monitor concomitant causes of GI toxicity, malabsorption/lactose intolerance, fecal impaction, dietary supplements high in fiber, and medications (e.g., stool softeners, laxatives, and antacids).

It is advised to discontinue all lactose-containing products, alcohol, and high osmolar supplements. Patients should be instructed to eat frequent small meals that include food with anti-diarrheal properties such as bananas, rice, apples, and toast. If Grade ≥ 2 diarrhea occurs, electrolytes need to be monitored at least daily and adequate hydration may be achieved if necessary through IV fluids for electrolyte correction.

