4.3 DOSE JUSTIFICATION

During Phase 1 development, two formulations were tested: microprecipitated bulk powder (MBP) and spray-dried powder (SDP); the relative bioavailability of SDP to MBP is approximately 2. For clarity, the doses of MBP tested have been re-designated to SDP equivalent (SDP eq) in this section.

Serum levels of macrophage inhibitory cytokine (MIC-1), a secreted protein that is strongly induced by activated p53, have been used to assess pharmacodynamic effects of idasanutlin in Phase 1 studies NP27872 and NP28679 (see [Idasanutlin IB](#)). Analysis of patients on 50 to 400 mg (SDP eq) daily × 5 days idasanutlin showed that the minimum level for p53 induction occurs at a dose of 50 mg (SDP eq)/day or a corresponding plasma level of 500 ng/mL of idasanutlin. In comparison, a weekly dosing schedule had a less pronounced effect on MIC-1.

A comparison of MIC-1 elevation between the idasanutlin dosing schedules demonstrated limited ability to activate p53 with the weekly schedule. The daily × 3 days dose regimen did not achieve steady-state exposure, displayed shorter duration for SD (median 57 and 103 days for daily × 3-day and daily × 5-day schedules, respectively), and did not alleviate thrombocytopenia. Therefore, the daily × 5-day schedule was chosen as optimal for future clinical trials.

In a study of idasanutlin-treated patients with solid tumors, NP27872, the 5-day schedule MTD was determined to be 250 mg (SDP eq) QD, in a 28-day cycle. Thrombocytopenia, neutropenia, febrile neutropenia and diarrhea were dose-limiting toxicities (DLTs). PK and safety data showed that there was an apparent pharmacokinetic/pharmacodynamic relationship between an AUC per cycle and Cycle 1 platelet nadir. In the AML study, NP28679, a protocol-defined MTD, with or without concomitant 1 g/m² cytarabine, was not achieved. Instead, 300 mg (SDP eq) BID for 5 days in a 28-day cycle was determined to be the maximum tolerable threshold based on GI tolerability.

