6.6 DOSAGE MODIFICATION

Intra-patient dose-escalation from 150 mg to 200 mg is allowed after Cycle 3 (*preferable at Cycle 4, or latest, Cycle 5*) for patients who have demonstrated adequate tolerability and are showing a lack of Hct control *and/or inadequately controlled leukocytosis and/or thrombocytosis* at end of Cycle 3 (Section 4.1.2). Patients with PD will not be permitted to dose-escalate and should come off the study. Consideration for dose-increase will be based on a review of patient data, including but not limited to, safety data, response assessments and laboratory data. All intra-patient dose-escalation decisions will be

made in consultation with the Investigator and Sponsor, including the Medical Monitor and Safety Science Leader.

In case of hematologic toxicity (i.e., anemia, thrombocytopenia and/or neutropenia), patients may need treatment interruptions and/or dose reductions (see Table 8).

Guidance for dose-reductions for AEs is described in Section 8.3.9. Furthermore, after one year of treatment (end of Cycle 13), a reduction of the idasanutlin dose to 100 mg for all subsequent cycles may occur for any patient that has not previously had a reduction to 100 mg for other reasons to generate data for longer term tolerability. This reduction will be based on communication between the Investigator and Sponsor. Treatment may be re-escalated back to the prior highest tolerated dose if Hct increases to $\geq 45\%$ and/or CHR response is lost ($WBC \geq 10 \times 10^9/L$ and PLT count $> 450 \times 10^9/L$) to achieve a hematologic response. Treatment *must* not be re-escalated if the patient has progressive disease (see Appendix 1).

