7.1.1 Temporary Interruption and Discontinuation

Table 6 shows the general guidance for dosing delay due to AEs. For details of temporary interruption secondary to specific AEs, see Section 8.3.9.

Table 6 General Guidance for Dosing Delay

Clinical Event Grade	
1	No dose modification required. ^a
2	No dose modification necessary. ^a
3	Duration ≤ 2 weeks: Hold further dosing until resolution to Grade ≤ 1 and then, resume at original dose or 100 mg. ^{b, c, d} Duration > 2 weeks, but ≤ 4 weeks: dose reduce to 100 mg. ^d Duration > 4 weeks: discontinue treatment. ^e
4	Duration ≤ 4 weeks: Hold further dosing until resolution to Grade ≤ 1, resume at 100 mg. ^d Duration > 4 weeks: discontinue treatment. If the Grade 4 AE recurs (a second time), then idasanutlin should be discontinued.

AE = adverse event.

- ^a Grade 1 or 2 AEs do not necessarily require dose holding or modification unless specifically noted in Table 8 (Guidelines for Managing Hematologic Toxicity). For Grade 2 events, idasanutlin can be resumed at the same dose when the event resolves to at least Grade 1.
- ^b Dose-reduction is allowed to 100 mg idasanutlin if by collective Investigator and Sponsor judgment that such a change is warranted.
- ^c Patients with Grade 3 AEs that are clearly unrelated to the study drug in the opinion of the Investigator and Sponsor and for which restarting/continuing idasanutlin does not pose a safety risk are allowed to continue receiving therapy without a necessary dose hold or modification.
- ^d If the patient is on 200-mg dose level, idasanutlin will resume at 150 mg (i.e., 50 mg dose reduction).
- ^e The decision to extend the dose delay will be made on the basis of the Investigator's assessment of ongoing clinical benefit and in consultation with the Medical Monitor.

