8.3.9.2 Management of Hematologic Toxicity and Risk of Infections

Idasanutlin has exposure-dependent suppressive effects on bone marrow progenitors and thus a balance between the desired effects on PV progenitor cells and the normal cells must be targeted. At the dose levels used in this study, a significant reduction in the counts of normal blood cells is not expected to be observed. Specific guidelines to manage the risk of hematologic toxicity are provided in [Table 8](#).

Frequent monitoring of hematologic values (count of blood cells, including differential) is recommended. See [Table 8](#) for guidelines for the management of hematologic toxicity.

Increased hemorrhagic risk should be proactively managed following institutional guidelines in case of Grade ≥ 2 thrombocytopenic events.

In case of a patient showing ANC count $< 1.0 \times 10^9/L$ and concomitant fever, idasanutlin should be permanently discontinued, *unless AEs are clearly unrelated to the treatment*. Similarly, in case of a Grade ≥ 3 systemic infection associated with any grade leukopenia (refer to [Appendix 12](#) for the list of PT considered pertinent to leukopenia) idasanutlin should be permanently discontinued, *unless AEs are clearly unrelated to the treatment*.

Table 8 Guidelines for Managing Hematologic Toxicity

Hgb level	ANC / PLT level	Management

Hgb ≥12 g/dL (women), 13 g/dL (men) (>7.5mmol/L [women]; >8.1 mmol/L [men]) AND
	
PLT ≥120 ×10⁹/L AND ANC ≥1.5 ×10⁹/L
	
 No dose modifications required.
	
PLT 75 to <120 ×10⁹/L AND ANC ≥1.5x10⁹/L
	
 Interrupt dose until PLT ≥120 ×10⁹/L. Resume with reduced idasanutlin dose with a 50-mg dose reduction (lowest idasanutlin dose is 100 mg; no dose modification required, if dose is already at 100 mg). If the event does not resolve within 28 days, discontinue treatment. ^a Monitor labs at least every 2 weeks until PLT ≥120 ×10⁹/L.

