8.3.9.3 Management of Other Toxicities

Oral administration of idasanutlin was associated with body weight loss and/or reduced body weight gain associated with decreased food consumption in preclinical safety toxicology studies performed in cynomolgus monkeys. Decreased appetite and anorexia have been commonly reported during idasanutlin clinical development. It is recommended to investigators to monitor weight and intervene with nutritional support if required.

Fatigue and asthenia are common clinical signs associated with PV. During clinical development of idasanutlin, fatigue and asthenia were commonly observed and can be interrelated with GI toxicity and decreased appetite/anorexia. It is recommended to investigators to monitor root cause and intervene on underlying causes with nutritional support as clinically required.

Idasanutlin has hepatic toxicity as a potential risk. Accordingly, ALT, AST and bilirubin will be monitored throughout the trial as specified in Section 1.2 and will be captured as AESI as specified in Section 8.3.6. Patients at screening also need to have adequate hepatic function as described in the inclusion criteria (Section 5.1). Patients with active hepatitis will not be eligible for treatment as per Exclusion Criteria (Section 5.2). In the case of abnormal liver function test during the trial, patients will be managed as described in Table 6.

In previous clinical studies, electrolyte disorders (reported with the following PTs: hypercalcaemia, hyperkalaemia, hypernatraemia, hypocalcaemia, hypokalaemia, hypomagnesaemia, hyponatremia, hyperphosphataemia, hypophosphataemia) very commonly occurred in patients treated with idasanutlin. Patients with clinically significant electrolyte abnormalities as per exclusion criteria (Section 5.2) will not be allowed to start idasanutlin treatment. Treatment for correction of above electrolyte imbalances is permitted during screening to meet eligibility. On treatment, electrolytes need to be frequently monitored and any eventual imbalances promptly corrected as per local medical guidelines.

The management of toxicity not listed in Table 7 or Table 8 will be managed as described in Table 6.

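### Protocol Table 7 gives two different doses after a second Grade ≥3 diarrhea in a patient who was on 200 mg at the first event (wrong as written, low severity)

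*Protocol*

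**What the plan says.** All references are to the Protocol.

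- **Escalation (Section 6.6).** "Intra-patient dose-escalation from 150 mg to 200 mg is allowed after Cycle 3". Section 4.1.2 makes this a joint decision of the investigator and the sponsor, for patients with adequate tolerability.
- **First Grade ≥3 diarrhea (Section 8.3.9.1, Table 7).** Dosing is held until Grade ≤1. If that takes no more than 28 days, "study drugs may be re-started with idasanutlin with a 50 mg dose reduction (lowest idasanutlin dose is 100 mg").
- **Second Grade ≥3 diarrhea despite supportive care and the reduction (Table 7).** Dosing is held again. If recovery takes no more than 28 days, "then the idasanutlin dose will be maintained at the previously reduced dose of 100 mg".
- **Third Grade ≥3 diarrhea (Table 7).** Permanent discontinuation.
- **General rule for dosing delays (Section 7.1.1, Table 6, footnote d).** "If the patient is on 200-mg dose level, idasanutlin will resume at 150 mg (i.e., 50 mg dose reduction").
- **Scope of Table 6 (Section 8.3.9.3).** "The management of toxicity not listed in Table 7 or Table 8 will be managed as described in Table 6".
- **Dose levels (Section 6.1, Table 4).** 150 mg, with possible escalation to 200 mg, and 100 mg if the dose is reduced.

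**The concern.** The second-event sentence names its dose in two ways: as the dose the patient was already reduced to, and as 100 mg. The two coincide only if the first reduction ended at 100 mg. For a patient who was on 200 mg, it ended at 150 mg.

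This is the re-dosing rule after a second severe episode of a toxicity that the protocol links to dose. Section 8.3.9 says: "Thrombocytopenia and GI toxicity are dose/exposure dependent but are not expected to occur as severe events at the dose levels investigated in this study". For the solid-tumor study, in which the five-day-schedule maximum tolerated dose (MTD) was 250 mg, Section 4.3 reports: "Thrombocytopenia, neutropenia, febrile neutropenia and diarrhea were dose-limiting toxicities (DLTs"). What is at stake is whether the escalated patient gets a second reduction step. If the dose is kept at 150 mg, a third event ends treatment without 100 mg having been tried. If 100 mg is given, the patient has that step first. A site that picks either dose departs from half of the sentence.

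**Working it through.** There is no published figure to reproduce; the check traces the dose rule in Table 7.

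**Inputs.** Possible doses are 100, 150 and 200 mg (Table 4 and Section 6.6). The first-event reduction is 50 mg with a floor of 100 mg (Table 7). The stated second-event dose is 100 mg (Table 7). The reference MTD is 250 mg (Section 4.3). Dosing is on five days per cycle (Section 6.1).

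**Rule.** Dose after the first event = max(dose at first event − 50, 100). If the dose is maintained, the dose after the second event is the same.

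| Dose at first event | After first event | After second event, if maintained | After second event, as the number states | Agree? |
|---|---|---|---|---|
| 100 mg | max(50, 100) = 100 mg | 100 mg | 100 mg | yes |
| 150 mg | max(100, 100) = 100 mg | 100 mg | 100 mg | yes |
| 200 mg | max(150, 100) = 150 mg | 150 mg | 100 mg | **no, 50 mg apart** |

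The conflict therefore arises only for a patient on 200 mg at the first event and still on 150 mg at the second.

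**Does other text settle it?**

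- Table 6, footnote d, addresses the 200-mg level, but Section 8.3.9.3 confines Table 6 to toxicities outside Tables 7 and 8. It would in any case give only the first step, 200 to 150 mg.
- Table 4 lists 100 mg as the reduced dose, but Table 7's own first step sends a 200-mg patient to 150 mg, so Table 4 cannot be read as the only reduced dose.
- Section 6.6 refers reductions for adverse events back to Section 8.3.9, which contains Table 7.

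**Size of the dose difference.**

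- Per cycle: 5 × 150 = 750 mg against 5 × 100 = 500 mg. The difference is 250 mg, and 250/750 = 33% of the higher dose.
- Relative to the 250-mg MTD: 200/250 = 80%, 150/250 = 60%, 100/250 = 40%.

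**How often.** The documents give no rate for the affected case. Section 2.3 reports diarrhea in 7 of 12 patients with polycythemia vera or essential thrombocythemia treated at 100 or 150 mg. There were 22 events, 3 of them Grade 2 and the other 19 Grade 1, so no patient had Grade ≥3. Those data concern lower doses and do not bear directly on repeat events after escalation to 200 mg.

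**The case against.** The strongest reply is that this is a drafting slip with an obvious answer. The sentence contains one number, 100 mg. It is also Table 7's lowest dose and the reduced dose in Table 4, and a site that follows it does what the fix below would ask. This stands as a reason for low severity and for choosing 100 mg in the correction. It does not make the sentence right: if the number governs, the words about maintaining the earlier reduced dose are false for this patient.

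Sponsor involvement is the second reply, and it also stands as mitigation. Escalation is agreed with the sponsor (Sections 4.1.2 and 6.6). Grade ≥3 gastrointestinal toxicity is an event of special interest, reportable within 24 hours (Section 8.3.7). Immediate safety concerns go to the sponsor (Section 8).

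Three stronger readings are tempting, and the documents do not support them.

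- **That resuming at the dose of recurrence is itself a defect.** Table 7 does this by design for every patient who started at 150 mg: reduced to 100 mg, recurrence at 100 mg, resumption at 100 mg. The only open question for the 200-mg patient is whether there is a further reduction step.
- **That Table 8 supplies a template Table 7 failed to copy.** One part of Table 8 does work at every dose level: "lowest idasanutlin dose is 100 mg; no dose modification required, if dose is already at 100 mg". But two rows of its second hemoglobin block discontinue treatment on recurrence, so there too a patient reduced from 200 to 150 mg may never try 100 mg. Table 8 is not uniform.
- **That Section 8.3.9.2 contradicts Table 8 on neutrophils below 1.0 × 10⁹/L with fever.** The text excepts events clearly unrelated to treatment and the table does not repeat the exception. The text stands directly before the table in the same section, and a site that stops treatment complies with both. If the exception applies, the existing row for neutrophils of 0.5 to below 1.5 gives the next step. Deleting the exception and extending it would be opposite clinical policies, and the documents do not show which is wanted.

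**Conclusion.** Table 7 is internally inconsistent for one group: patients on 200 mg at their first Grade ≥3 diarrhea. It leads to 150 mg by one half of the second-event sentence and to 100 mg by the other. It is consistent for patients at 150 or 100 mg.

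The conclusion rests on reading Table 7's first-event reduction as applying from the patient's current dose, and on Section 8.3.9.3 keeping Table 6 out of diarrhea management. Both follow from the text.

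The label is wrong as written, low severity. The affected patient must have tolerated 150 mg well enough to be escalated and must then have two Grade ≥3 diarrheas, each resolving to Grade ≤1 within 28 days; the protocol does not expect severe gastrointestinal toxicity at these doses. A reader might infer that a dosing error of this kind affects the study's statistical case. It does not: no sample size, posterior probability, confidence limit, population definition or analysis rule depends on it.

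**What to change.** Replace the second-event sentence in Table 7 with:

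*If recovery occurs within 28 days, resume at 100 mg (a further 50-mg reduction if previously reduced from 200 to 150 mg; maintained if already at 100 mg).*

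This keeps the only dose the sentence now states and the floor already in Table 7. It changes nothing for patients who started at 150 mg. The rules for recovery beyond 28 days and for a third event stay as they are.

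The cost is one sentence at the next amendment, with no new assessments, data collection or analyses.
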